3.3.2 Removal of Patients from Therapy or Assessment

A premature discontinuation will occur when a patient who has signed the ICF ceases participation in the study, regardless of circumstances, before completion of the Treatment Period.

A patient will be considered to have completed the study after receiving 8 weeks of treatment and completing the End-of-treatment (EOT) Visit at Day 57. A window of +3 days will be allowed for the EOT visit; if a patient completes the EOT Visit prior to Day 57, this will be considered a protocol deviation.

Patients will be informed that they are free to withdraw from the study at any time and for any reason. The Investigator may remove a patient from the study if, in the Investigator's opinion, it is not in the best interest of the patient to continue the study. Patients may also be discontinued from the study by the Investigator or the Sponsor at any time for any reason, including the following:

- Failure to meet an inclusion/exclusion criterion that is clinically relevant and affects patient safety
- Adverse event(s)

- Protocol violation, including lack of compliance
- Insufficient therapeutic response (lack of efficacy)
- Lost to follow-up (every effort must be made to contact the patient; a certified letter must be sent)
- Withdrawal of consent (attempts should be made to determine the reason for the patient withdrawing consent if possible)
- Study termination by the Sponsor
- Other reasons (e.g., administrative reasons or pregnancy)

The date the patient is withdrawn from the study and the reason for discontinuation will be recorded on the study termination form of the electronic case report form (eCRF). Patients who discontinue from the study for any reason should complete the assessments required at the EOT Visit at the time of their discontinuation. Patients who discontinue from the study will be followed until resolution of all of their AEs or until the unresolved AEs are judged by the Investigator to have stabilized. Study centers should make a reasonable effort to follow any pregnant patients until delivery or end of the pregnancy.

If a patient does not return for a scheduled visit, the study center should contact the patient. An effort must be made to contact the patient, including sending a certified letter. In every case, the patient outcome, including lost to follow-up information, will be documented.

3.3.3 Replacement Procedures

Patients in this study who prematurely discontinue treatment will not be replaced.

3.4 STUDY TREATMENTS

3.4.1 Investigational Product

3.4.1.1 IW-3718

Study medication will be provided as 500 mg IW-3718 tablets which are white to off-white, oval shaped, film-coated tablets intended for oral administration. In addition to the active drug substance, colesevlam, 500 mg IW-3718 tablets contain the following inactive ingredients: microcrystalline cellulose, polyethylene oxide, colloidal silicon oxide, butylated hydroxyl

toluene, magnesium stearate, polyvinyl alcohol, polyethylene glycol, titanium dioxide, and talc. Tablets should be taken whole and never broken, crushed, or chewed.

Patients randomized to receive IW-3718 will administer the test product as follows:

- 500 mg IW-3718 BID: One 500 mg IW-3718 oral tablet plus 2 placebo oral tablets (3 tablets total) administered BID, immediately after the morning and evening meals
- 1000 mg IW-3718 BID: Two 500 mg IW-3718 oral tablets plus 1 placebo oral tablet (3 tablets total) administered BID, immediately after the morning and evening meals
- 1500 mg IW-3718 BID: Three 500 mg IW-3718 oral tablets administered BID, immediately after the morning and evening meals

3.4.1.2 Placebo

Placebo to match 500 mg IW-3718 tablets will be provided as white to off-white, oval shaped, film-coated, oral tablets containing microcrystalline cellulose, polyethylene oxide, colloidal silicon oxide, butylated hydroxyl toluene, magnesium stearate, polyvinyl alcohol, polyethylene glycol, titanium dioxide, and talc. Tablets should be taken whole and never broken, crushed, or chewed.

Patients randomized to receive placebo will administer the test product as follows:

- Three oral placebo tablets will be administered BID immediately after the morning and evening meals.

3.4.1.3 Rescue Medicine

Antacid rescue medicine will be provided to the clinical site as a bottled liquid (magnesium hydroxide 200 mg/aluminum hydroxide 200 mg per 5 mL).

During completion of the PDA daytime and nighttime diary questions, patients will be asked about their rescue medicine use by responding to the following questions:

- “How many times did you use your rescue medicine (liquid antacid) from the time you got out of bed this morning until now?” (Daytime assessment, completed at night before going to bed)

- “How many times did you use your rescue medicine (liquid antacid) last night?” (Nighttime assessment, completed in the morning)

3.4.1.4 Treatment Compliance

Patients will be dispensed the appropriate number of Sponsor-packaged, labeled blister wallets needed until the next study visit (see Section 3.6). Patients will be asked to return all blister wallets (including unused tablets) at each study visit for assessment of compliance with the dosing regimen.

Patients will record their PPI administration each day (once daily) in their eDiary.

3.4.2 Packaging and Labeling

Study medication (IW-3718 and placebo tablets) will be provided by Ironwood as 60 count blisters in wallets, indicating morning and evening doses. Study medication will be uniquely numbered and labeled in a double-blind fashion that conforms to regulatory requirements.

3.4.3 Storage and Stability

Study medication (IW-3718 and placebo tablets) will be shipped at refrigerated temperatures between 2°C and 8°C (36°F and 46°F) and must be stored at refrigerated temperatures between 2°C and 8°C (36°F and 46°F). Antacid rescue medicine will be shipped at room temperature between 20°C and 25°C (68°F and 77°F) and must be stored at room temperature between 20°C and 25°C (68°F and 77°F). Any deviation from these storage conditions must be reported to Ironwood and use of the study medication suspended until authorization for its continued use has been provided by Ironwood.

The Investigator must ensure that the receipt and use of all study medication supplied is recorded and must supervise the storage and allocation of these supplies. All study medication supplies must be retained in a locked room that may only be accessed by the Investigator, or other duly designated persons. Study medication must not be used outside the context of this protocol, and under no circumstances should the Investigator or study center personnel allow the supplies to be used other than as directed by this protocol without prior authorization from Ironwood.

3.4.4 Method of Assigning Patients to Treatment Groups

Patients who meet all of the inclusion criteria and none of the exclusion criteria will be randomized into the study on Day 1. Patients will be stratified by whether they have or do not have erosive esophagitis on the screening EGD then randomized through central randomization in a 1:1:1:1 ratio to receive either 500 mg IW-3718 BID, 1000 mg IW-3718 BID, 1500 mg IW-3718 BID, or placebo BID.

The computer-generated randomization schedule will be prepared by an independent statistician not otherwise associated with the study.

3.4.5 Selection of Dosage in the Study

During this study, oral doses of IW-3718 at 500 mg BID (total daily dose of 1000 mg/day), 1000 mg BID (total daily dose of 2000 mg/day), and 1500 mg BID (total daily dose of 3000 mg/day) given as an adjunct to QD PPI for 56 days will be studied in order to evaluate the dose-response relationship for IW-3718 in a placebo-controlled study. The 1000 mg BID dose was used in a previous Phase 2a study (Study ICP-3718-201) and provided a reasonable level of efficacy with an acceptable safety and tolerability profile. The highest dose level (1500 mg BID) was chosen to determine whether it can provide a higher level of efficacy with an acceptable safety profile. The lowest dose level (500 mg BID) will be included since it may demonstrate efficacy, and will allow for a more accurate assessment of the dose-response relationship for IW-3718. This could support the proof-of-concept for efficacy and support further evaluation of IW-3718 in Phase 3 studies with any of the 3 dose levels. In addition to assessing efficacy for each dose group, the safety profile at all 3 doses will also be evaluated.

3.4.6 Selection and Timing of Dose for Each Patient

Patients will be randomized to receive 500 mg IW-3718 BID, 1000 mg IW-3718 BID, 1500 mg IW-3718 BID, or placebo BID. The first dose of study medication will be taken with liquid and a snack in clinic at the Randomization Visit (on Day 1). Patients should take their second dose that evening immediately upon completion of dinner, ensuring that at least 8 hours have elapsed since the first dose in clinic.

During the Treatment Period, patients will take study medication BID at home, in the morning (immediately upon completion of breakfast) and in the evening (immediately upon completion of dinner), even on study visit days. The last dose of study medication will be taken the morning of the EOT Visit.

Additionally, all patients will take their current PPI during the Pretreatment, Randomization, and Treatment Periods (i.e., Day -21 through Day 57 [+ 3 days]). The PPI will be taken each day, approximately 30-60 minutes before breakfast.

During completion of the PDA daily diary questions, patients will be asked to confirm daily dosing of their PPI by responding to the following question:

- “Did you take your PPI this morning?”

3.4.7 Blinding

This study is double-blind and placebo-controlled. The Sponsor, Investigator, and study center staff will be blinded to treatment assignments.

Unblinding of a patient’s treatment assignment is restricted to emergency situations and should only be used under circumstances where knowledge of the treatment is necessary for the proper handling of the patient. Except in a medical emergency, the Investigator and blinded study center staff will remain blinded during the conduct of the study and until such time that all discrepancies in the clinical database are resolved (i.e., at the time of the database lock).

Individual patient treatment assignment unblinding is available to the Investigator through the interactive web response system (IWRS) in the event of an emergency. The Investigator should make all reasonable efforts to notify and discuss the circumstances requiring unblinding with the Medical Monitor or designee in advance of breaking the blind. If the treatment blind is broken, the reason and the date should be recorded and signed by the Investigator and information regarding the unblinding should be submitted as soon as possible to the Sponsor. The patient will be immediately withdrawn from the study if the code is broken.

The Sponsor may also break the blind in circumstances where unblinding is necessary for the safety of the patients.

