1.2 IW-3718

Ironwood is developing IW-3718 for the treatment of symptomatic GERD not completely responsive to PPIs and for and other gastrointestinal (GI) disorders. IW-3718 is colesevelam hydrochloride (HCl), a bile acid sequestrant (BAS).

Colesevelam HCl (hereafter referred to as colesevelam) is an orally administered, nonabsorbed, nondigestible polymer that binds bile acids in the GI tract. Colesevelam was approved in 2000 in the United States (US) as the active ingredient in Welchol™, and is indicated as an adjunct to diet and exercise for reduction of elevated low-density lipoprotein cholesterol (LDL-C) in adults with primary hyperlipidemia. Colesevelam is currently available as an immediate-release formulation only.

IW-3718 tablets are formulated as a controlled-release, solid oral dosage form intended to extend the release of the drug substance, colesevelam, into the stomach. The released colesevelam is expected to bind bile acids that are refluxed into the stomach and upper duodenum, forming a bile acid-colesevelam complex and preventing the free bile acids from entering the esophagus. The bile acid-colesevelam complex will travel down the GI tract and be excreted without being absorbed.

The controlled-release formulation in IW-3718 tablets is based on Depomed's Acuform® technology which utilizes swelling polymers to allow the tablet to be retained in the stomach for approximately 9 hours when dosed in the fed state, during which time the tablet slowly releases the active ingredient in the stomach and upper GI tract. The tablet's active ingredient is steadily delivered to the stomach and upper GI tract in a near zero-order manner. The technology is used in the formulation of 5 Food and Drug Administration (FDA)-approved drugs: Glumetza® (metformin HCl, extended release), Janumet® XR (sitagliptin and metformin HCl extended-

release), Proquin® XR (ciprofloxacin HCl monohydrate, extended release), NUCYNTA® ER (tapentadol extended-release tablets), and once-daily Gralise™ (gabapentin) tablets.

Colesevelam is not systemically absorbed and does not interfere with systemic drug metabolizing enzymes. Distribution of colesevelam is limited to the GI tract and elimination occurs through fecal excretion.

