Colesevelam reduces serum LDL-C concentrations by binding bile acids in the intestine, impeding their reabsorption. As the bile acid pool becomes depleted, the hepatic enzyme, cholesterol 7- α -hydroxylase, is upregulated, which increases the conversion of cholesterol to bile acids. This causes an increased demand for cholesterol in the liver cells, resulting in the dual effect of increasing transcription and activity of the cholesterol biosynthetic enzyme, HMG-CoA reductase, and increasing the number of hepatic LDL receptors. These compensatory effects result in increased clearance of LDL-C from the blood, resulting in decreased serum LDL-C concentrations. Serum triglyceride concentrations may increase or remain unchanged. The mechanism by which colesevelam improves glycemic control is unknown. However, increasing evidence suggests that colesevelam, as a BAS, may function by signaling molecules in the liver and GI tract for lipid and glucose metabolism (13,14,15,16). The mechanism by which colesevelam is expected to reduce symptoms in GERD is by binding bile acids that are refluxed into the stomach and preventing the free bile acids from entering the esophagus and reacting with the esophageal mucosa.

There are no reported clinical efficacy studies with colesevelam in patients with GERD, or other upper GI disorders.

Colesevelam (as Welchol) has been evaluated for safety in clinical studies and via post-marketing pharmacovigilance. In general, colesevelam was safe and well-tolerated in adults with hyperlipidemia or type 2 diabetes mellitus, and in adolescents with familial hypercholesterolemia. Due to the large doses required for lipid lowering, and its local effects in the GI tract, most of the adverse events (AEs) related to colesevelam are GI in nature (constipation, flatulence, and dyspepsia). Most of these AEs were of mild or moderate intensity. In clinical lipid-lowering studies, the incidence of dyspepsia was greater at the higher doses (3.8 and 4.5 g/day).

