3.5.1.8 Clinical Laboratory Determinations

Blood and urine samples for clinical laboratory tests will be collected at the visits defined in the Schedule of Events ([Table 2](#)). The clinical laboratory evaluations will include the clinical chemistry, hematology, coagulation, and urinalysis parameters presented in [Table 1](#).

Table 1. Clinical Laboratory Tests

Clinical Chemistry	Hematology (CBC)	Complete Urinalysis
A1C	Hematocrit	pH and specific gravity
Albumin	Hemoglobin	Bilirubin
Alkaline phosphatase	Platelet count	Glucose
ALT	MPV	Ketones
AST	RBC count	Leukocytes
Bicarbonate	WBC count	Nitrites
BUN	WBC differential	Occult blood
Calcium	(% and absolute)	Protein
Chloride	Basophils	Urobilinogen
Total cholesterol	Eosinophils	
HDL cholesterol	Lymphocytes	
LDL cholesterol	Monocytes	
Creatinine	Neutrophils	
GGT	RBC indices	
Glucose	MCH	
Iron	MCHC	
LDH	MCV	
Magnesium	RDW	
Phosphorus	Coagulation	
Potassium	aPTT	
Sodium	PT	
Total bilirubin		
Total protein		
Triglycerides		
Uric acid		

Abbreviations: A1C = glycated hemoglobin; ALT = alanine aminotransferase; aPTT = activated partial thromboplastin time; AST = aspartate aminotransferase; BUN = blood urea nitrogen; CBC = complete blood count; GGT = gamma glutamyl transferase; HDL = high-density lipoprotein; LDH = lactate dehydrogenase; LDL = low-density lipoprotein; MCH = mean corpuscular hemoglobin; MCHC = mean corpuscular hemoglobin concentration; MCV = mean corpuscular volume; MPV = mean platelet volume; PT = prothrombin time; RBC = red blood cell; RDW = red cell distribution width; WBC = white blood cell

A blood sample for serum pregnancy testing will be collected from all female patients of childbearing potential (i.e., women who are not postmenopausal or who have not had a bilateral oophorectomy, hysterectomy, or tubal ligation) at the Screening and EOT Visits, and a urine sample will be collected at the Randomization Visit (prior to dosing) and the Week 4 Visit.

These pregnancy test results must be negative for patient eligibility. Ironwood may perform non-genetic analyses on existing plasma or serum samples for research purposes (e.g., bile in serum).

A urine screen for selected drugs of abuse (cocaine, barbiturates, amphetamines, opiates, benzodiazepines, and cannabinoids) and a serum alcohol screen will be performed at the Screening Visit.

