3.6 SCHEDULE OF EVENTS

The schedule of study procedures and assessments is presented by visit in the Schedule of Events in [Table 2](#).

Table 2. Schedule of Events

	Screening Period (Up to 4 weeks)^w	Pretreatment Period (2 weeks)	Treatment Period (8 weeks)				Follow-up
Visit Days →	Screening Visit (Day -49 to Day -15)	Pretreatment Visit (Day -21 to Day -1)	Randomization Visit (Day 1)	Week 2 Visit (Day 15 ± 3)	Week 4 Visit (Day 29 ± 3)	Week 8 / End-of-treatment Visit (Day 57 ± 3)	EOT + 7 days
Visit Numbers →	Visit 1	Visit 2	Visit 3	Visit 4	Visit 5	Visit 6	
Study Procedure ↓							
Inclusion and Exclusion Criteria Verification	X	X	X				
Signing of ICF	X						
IWRS Registration (a)	X	X	X	X	X	X	
Medical History	X						
Demographics	X						
Physical Examination (b)	X						X
Body Weight and Height (c)	X	X	X	X	X	X	
H2RA/Antacid Washout (d)	X						
Bilitec Monitoring (e)	X						
EGD (f)	X						X
48 to 96 Hours of pH Testing with Bravo Device (g)	X						
Seated Vital Signs (h)	X	X	X	X	X	X	
12-Lead ECG (i)	X		X				X
Prior and Concomitant Medications (j)	X	X	X	X	X	X	
Clinical Laboratory Tests(k)	X		X		X	X	
Serum Pregnancy Test (l)	X						X
Urine Pregnancy Test (l)			X		X		

Table 2. Schedule of Events

	Screening Period (Up to 4 weeks) ^w	Pretreatment Period (2 weeks)	Treatment Period (8 weeks)				Follow-up
Visit Days →	Screening Visit (Day -49 to Day -15)	Pretreatment Visit (Day -21 to Day -1)	Randomization Visit (Day 1)	Week 2 Visit (Day 15 ± 3)	Week 4 Visit (Day 29 ± 3)	Week 8 / End-of-treatment Visit (Day 57 ± 3)	EOT + 7 days
Visit Numbers →	Visit 1	Visit 2	Visit 3	Visit 4	Visit 5	Visit 6	
Study Procedure ↓							
Drug and Alcohol Screen (m)	X						
AE Evaluations (n)	X	X	X	X	X	X	
Rescue Medicine Dispensed (o)		X	X	X	X		
PDA Training and Dispensation		X					
Saliva Collection (p)	X	X	X		X	X	
eDiary (q)		X	X	X	X	X	
Weekly Symptom and Treatment Assessments (r)		X	X	X	X	X	
GSRS-Self			X		X	X	
QIDS-SR-16			X				
SF-12V2			X		X	X	
EQ-5D-3L			X		X	X	
Randomization			X				
Study Medication Dispensed (s)			X	X	X		
Study Medication Return (t)				X	X	X	
PDA Return						X	
mRESQ Debrief Interview (x)		X (x)			X (x)		
End-of-treatment Question (u)						X	
Safety Follow-up Call (v)							X

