3.6.2.1 Randomization Visit (Visit 3) Procedures

- Register visit in IWRS
- Review of inclusion and exclusion criteria
- Body weight
- Seated vital signs
- 12-lead ECG
- Concomitant medications
- Collection of blood and urine samples for clinical laboratory tests, including:
 - Clinical chemistry
 - Hematology (CBC)
 - Coagulation
 - Urinalysis
- Urine pregnancy test for all females of childbearing potential (must be confirmed negative prior to dosing)
- AE evaluation (throughout the Treatment Period)
- Antacid rescue medicine dispensation (if needed)
- Saliva collection
- Collect PDA and review eDiary
- GSRS-Self
- QIDS-SR-16
- SF-12V2
- EQ-5D-3L
- Randomization
- Study medication dispensed
- Study medication administration (first dose of study medication taken in clinic with liquid and a snack. Patients should take their second dose that evening, with liquid, immediately upon completion of dinner and ensure that at least 8 hours have elapsed since the first dose in clinic).

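### Does the unmasked Week 4 cholesterol panel endanger the blind enough to require a change?

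*Protocol*

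**What the plan says.** Protocol section 3.4.7 says "The Sponsor, Investigator, and study center staff will be blinded to treatment assignments". The rest of that section deals with emergency unblinding and database lock and does not mention laboratory results.

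Protocol section 1.2 identifies IW-3718 as colesevelam and states that "Colesevelam reduces serum LDL-C concentrations by binding bile acids in the intestine, impeding their reabsorption". The same section qualifies this. The approved lipid use is "reduction of elevated low-density lipoprotein cholesterol (LDL-C) in adults with primary hyperlipidemia", and the account of side effects begins "Due to the large doses required for lipid lowering". It also notes that "Serum triglyceride concentrations may increase or remain unchanged".

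Table 1 in section 3.5.1.8 includes "LDL cholesterol", with total and HDL cholesterol and triglycerides. The panel is drawn at Screening, Randomization (section 3.6.2.1: "Collection of blood and urine samples for clinical laboratory tests, including" clinical chemistry), Week 4 and Week 8/EOT. Section 3.5.1.3 asks the investigator to judge whether laboratory abnormalities are adverse events and makes no exception for lipids. The only result the protocol masks is Bilitec, and only from patients (section 3.1).

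**The concern.** A drug with a known laboratory effect can reveal itself through routine safety bloods. Here the protocol names the effect, measures it before treatment and about four weeks into treatment, and appears to return the values to the person who rates adverse events. An investigator who sees a clear LDL fall may suspect active drug, and one who sees none may suspect placebo.

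Two things could be affected. The direct one is the causality rating required by Protocol section 3.5.1.1.1, because SAP section 5.12.1 tabulates treatment-emergent events related to study drug. The indirect one is the heartburn endpoint, if a site's belief reached the patient or influenced a withdrawal for lack of efficacy. Masking three analytes looks like a cheap precaution against both.

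**Working it through.** **1. Is the gap there?** Yes. No section of either document withholds post-randomization lipids. Equally, none says that sites or the sponsor receive LDL values during treatment. Section 3.5.1.3 implies laboratory review but not release of every analyte, and a laboratory manual could settle the matter.

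**2. Can the clue reach the primary endpoint?** The weekly heartburn score comes from a diary the patient completes at night (section 3.5.2.1.1). Week 4 is the only on-treatment draw before the Week 8 diary window, since the EOT draw comes after it. No visit is scheduled between Week 4 and EOT. What remains is unscheduled contact or withdrawal. Planned loss is 65 − 58 = 7 per arm, or 260 − 4 × 58 = 28 overall (section 3.7.7), for all causes over 8 weeks. The part that falls after Week 4 and is for lack of efficacy is unknown and no larger than this planned total.

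**3. How much adverse event follow-up comes after the Week 4 draw?** Nominal days are Week 4 = 29, EOT = 57 and follow-up call = 64.

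- Nominal: (64 − 29)/(64 − 1) = 35/63 = 55.6%.
- Lowest (draw Day 32, call Day 61): 29/60 = 48.3%.
- Highest (draw Day 26, call Day 67): 41/66 = 62.1%.

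These use the EOT window of ±3 days in Protocol Table 2; section 3.3.2 and the SAP schedule give +3 only. They are shares of calendar time, not of events or ratings, and they ignore laboratory turnaround.

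**4. How strong is the clue?** The documents give the direction of the LDL effect but neither its size nor its SD, so both are assumed. Allocation is 1:1:1:1 (section 3.4.4), so always guessing active is right 75.0% of the time.

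*Effect graded by dose.* The percent change in LDL is N(0, SD) on placebo and N(−d/3, SD), N(−2d/3, SD) and N(−d, SD) on the three doses. Best-guess accuracy = ∫ max(0.25·f_placebo, 0.25·Σf_active).

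| SD | d = 5% | d = 10% | d = 15% | d = 20% |
|---|---|---|---|---|
| 8% | 75.0 | 75.9 | 78.3 | 81.1 |
| 12% | 75.0 | 75.1 | 75.9 | 77.4 |
| 16% | 75.0 | 75.0 | 75.2 | 75.9 |
| 20% | 75.0 | 75.0 | 75.0 | 75.3 |

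The gain is 0 to 6.1 points, median 0.2, and at most 1.0 in 13 of 16 cells.

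*Same full effect at every dose.* The best cutoff is c = −d/2 + (SD²/d)·ln 3, and accuracy = 0.75·Φ((c + d)/SD) + 0.25·(1 − Φ(c/SD)). For d = 10 and SD = 12, c = −5 + 14.4 × 1.0986 = 10.8, so the rater should guess placebo only if LDL rises by more than 10.8%. Accuracy is 0.75 × 0.959 + 0.25 × 0.184 = 76.5%. Over the grid the gain is 0 to 16.4 points, median 1.9, and below 3 in 10 of 16 cells.

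Both models assume a rater who knows the shift, the SD and the best cutoff, which overstates what a real rater could do. Both use one draw only; the EOT panel might be back before the follow-up call, so the figures are not strict upper limits.

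**5. What would masking cost?** Week 4 cholesterol would reach the investigator only after the follow-up call: 61 − 32 = 29 to 67 − 26 = 41 days later. SAP Table 5.12-2 treats total cholesterol above 1.6 × ULN as potentially clinically significant, so masking would also need an alert route. The repeat fasted lipid panel in footnote k of the schedule could return the masked values and would have to be covered. Protocol section 7.1 allows for local laboratories, and section 5 plans 60 to 80 centers, so the masking might have to be arranged laboratory by laboratory.

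**The case for a change.** The best case for acting is that best-guess accuracy is a blunt measure. With a 75% prior, belief can move without the best guess changing, and causality rating depends on belief. If the active–placebo separation is s SDs and the cutoff is at the midpoint, sensitivity and specificity are both Φ(s/2), and the chance of active given a fall is 0.75Φ/(0.75Φ + 0.25(1 − Φ)). For s = 0.25, 0.5, 1.0 and 1.5 this is 79%, 82%, 87% and 91%, against 75% with no lipid information. Nor can a lipid effect be dismissed on dose alone: section 1.2 calls 3.8 and 4.5 g/day the higher lipid-lowering doses, and the top arm here takes 3 g/day, or 3/3.8 = 79% of the lower figure.

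This stands as far as it goes. The clue may exist, and the protocol could have said how it is handled. But the larger shifts need separations for which the documents give no support. Patients are not selected for raised LDL, the other arms take 1 and 2 g/day, the formulation is controlled-release, and the Week 4 draw follows breakfast and study drug. The output at risk is a two-category judgement reported descriptively, beside tables of all treatment-emergent events that do not use it. For the sponsor's blind no harm is identified, since no interim analysis is planned. Masking cholesterol would also leave triglycerides and constipation (13% versus 0% in Phase 2a) as clues.

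**Conclusion.** No change to the plan is called for. The protocol's silence on post-randomization lipids is real, but it contradicts nothing: section 3.4.7 blinds people to assignment, and a laboratory manual may already cover the results. The endpoint is scored by the patient at home and is largely insulated. The remaining exposure is causality rating over roughly half of the adverse event follow-up. There, a well-informed guesser gains a median of 0.2 points over 75% if the LDL effect is graded by dose, or 1.9 points if it is equal across doses, and nothing if there is no effect. The largest gains, 6.1 and 16.4 points, require a 20% top-dose reduction with an SD of only 8%. All of these figures rest on assumed LDL effects and SDs.

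Against that, masking delays safety review by 29 to 41 days, needs an alert route, may need separate arrangements with local laboratories, and closes only one of several clues. In a trial that Protocol section 3.7.2 calls exploratory, accepting this small leak is a fair trade-off.
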